Proprietary confidential information © 2023 Boehringer Ingelheim International GmbH or one or more of its affiliated companies

If the positive report is confirmed, appropriate actions for the patient's safety have to be initiated and followed up as deemed necessary. The C-SSRS may be repeated at an unscheduled visit at the investigator's descretion.

C-SSRS results will be reported in terms of AEs as described in Section 5.2.6.1.4.

Penn Physician Withdrawal Checklist (PWC-20) is a short, reliable instrument that has been developed to detect potential treatment discontinuation (withdrawal) symptoms [R20-4170]. This 20-item questionnaire will be administered first at visit 10 or at the early EOT visit, for patients who prematurely discontinue study drug, and then during the 4-week follow-up period after termination of treatment with Iclepertin to collect potential symptoms and AEs related to dependence and withdrawal in a structured manner. Collection of AEs should be done before administering the PWC-20. Note: for AE reporting in eCRF and on SAE form (when applicable) the standards as outlined in section 5.2.6 apply. Symptoms that are exclusively determined to be due to the underlying disease without presenting any worsening, do not require AE reporting.

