5.2.6.2 Adverse event collection and reporting

5.2.6.2.1 **AE** Collection

The investigator shall maintain and keep detailed records of all AEs in the patient files.

The following must be collected and documented on the appropriate eCRF(s) by the investigator:

For patients *who* roll-over to the extension trial:

o From signing informed consent (1346-0012) onwards until first dose of trial medication in the extension trial: all AEs (serious and non-serious) and all AESIs. Updates to concomitant therapy should also be included until first dose of trial medication in the extension trial.

Note: Updates for SAEs and/or AESIs that are ongoing at the time of rollover to the extension trial must also be updated in the parent trial (1346-0012) in addition to being recorded in the extension trial, as long as the database for the parent trial is not locked. On the SAE form, updates for events reportable on the SAE form with onset in the parent trial are only reported into the parent trial.

For patients who do not roll-over to the extension trial:

- From signing the informed consent onwards until the 28 days (Follow-up 6 visit) after the EOT visit: all AEs (serious and non-serious) and all AESIs.
- After the individual patient's end of study: The investigator does not need to actively monitor the patient for new AEs but should only report any occurrence of cancer and trial treatment related SAEs and trial treatment related AESIs of which the investigator may become aware of by any means of communication, e.g. phone call. Those AEs should be reported on the BI SAE form (see section 5.2.6.2.2), but not on the eCRF.

For patients who permanently discontinue trial medication prematurely

- From signing the informed consent onwards until the 28 days after the early EOT visit: all AEs (serious and non-serious) and all AESIs.
- From Follow-up visit 6 up to the individual patient's planned end of study: until the individual patient's planned end of the study, the investigator must report treatment related SAEs / AESIs and the following events regardless of causal relationship:
 - anaemia,
 - all SAEs from C-SSRS assessments,
 - any occurrences of cancer
 - all deaths/ fatal AEs.

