6.2.3.4 Early permanent discontinuation from treatment

- Every effort should be made to collect data in all randomised patients. This includes randomised patients who never took the study medications and patients who permanently discontinued study drug.
- If a patient permanently discontinues the study medication, an eEOT visit must be performed within 7 days after the last dose of study medication. It is extremely important that patient should be encouraged to complete at least the MCCB, SCoRS and VRFCAT assessments. The reason for discontinuation of treatment must be recorded in the eCRF.
- The eEOT Visit can be split into 2 sequential days, in which case:
 - o The MCCB and VRFCAT should be performed on the first day;
 - o PRECIS should not take place immediately after MCCB, to avoid bias.

Page 74 of 112

- o The remaining assessments can be done per the convenience of the patient and site, either on the first day or the second day of the eEOT visit.
- To reduce burden on study partner, it is recommended to perform SCoRS on the same day.

- After the eEOT visit, patients should complete the safety follow-up visits and continue with the scheduled trial visits, until the end of the planned end of trial for that patient unless they withdraw consent to participate in the study.
 - o Refer to the Retention Guide in your ISF for further instructions.
- If it is not possible to complete all visits in clinic, at least phone contacts should occur at the scheduled visit time points. It is vital to explain to these patients the importance of continued trial participation. Additional information is provided in the ISF.
- When discussing options for continued trial participation, sites must present the first option to the patient and discuss this option thoroughly before presenting the next option for follow-up.
- Patients should be encouraged to choose the most rigorous follow-up regimen they are willing and able to comply with. The investigators should inform these patients that they will be allowed to change this regimen later if needed.
- Patients may choose to re-start the trial medication at any time during their planned treatment period as long as there is no safety concern, in the opinion of the investigator.

Table 6.2.3.4: 1 Follow-up of patients who prematurely discontinue the study treatment*

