In addition to the main safety analysis, withdrawal-related safety analysis will be conducted separately and descriptive for AEs emerging during the off-treatment safety follow-up period. New AEs emerging during this 4-week safety period, compared to while the patient is still on-treatment, will be identified and assessed by contrasting the following analysing treatment periods:

- 4-week withdrawal period for AEs occurring from 1 day after last dose to 28 after last dose of trial medication, and
- Strictly on-treatment period for AEs occurring from the start of treatment to the last dose of trial medication.

Page 84 of 112

Proprietary confidential information © 2023 Boehringer Ingelheim International GmbH or one or more of its affiliated companies

This withdrawal-related safety analysis will also assess vital signs descriptively.

Change in withdrawal symptoms based on PWC-20 will be analysed descriptively.

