#### 6. GENERAL ANALYSIS DEFINITIONS

## 6.1 TREATMENT(S)

For basic study information on treatments to be administered, assignment of treatment groups, select of doses, see CTP Section 4.

Table 6.1: 1 lists the two treatment groups in this study. Table 6.1: 2 defines the analysing treatment period for safety analyses. For this study, the residual effect period (REP) is defined as 12 days after the last dose of trial medication.

Table 6.1: 1 Treatment descriptions

Long Name	Short Name	
Placebo	Placebo	
Iclepertin 10 mg QD	Iclepertin 10 mg	

Table 6.1: 2 Analysing treatment periods (same for all treatment groups)

Analysing Treatment Period	Start Date	End Date
Screening period	Date of informed consent	Date of the first treatment administration – 1 day
On-treatment period	Date of the first treatment administration	Date of the last treatment administration + REP
Post-treatment period	Date of the last treatment administration + REP + 1 day	Date of the last per protocol visit
Strictly on-treatment period	Date of the first treatment administration	Date of the last treatment administration
4-week withdrawal period	Date of last treatment administration + 1 day	Date of last treatment administration + 28 day

REP is the residual effect period which is defined as 12 days after the last dose of trial treatment.

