#### 6.3 INTERCURRENT EVENTS

Definition and technical specification of protocol defined intercurrent events (ICEs) are listed in Table 6.3: 1. In general, when handled under the hypothetical approach, data collected during the off-treatment period of an ICE will be considered irrelevant to the estimand and excluded from the analysis. While off-treatment data will be excluded, the patient will still be

considered as on-treatment (hypothetically) from an analysis perspective by the statistical models, and during any imputations.

For an ICE of temporary treatment discontinuation or interruptions, the off-treatment period spans from the last treatment administration prior to the interruption + REP to the restart of the study medication. For an ICE of early permanent treatment discontinuation, the off-treatment period starts from the last treatment administration + REP. Figure 6.3: 1 illustrates the on-/off-treatment status after each type of ICEs. When there is more than one ICE of early permanent treatment discontinuation, any treatment policy ICE take precedence in data and analysis handling over any hypothetical ICE.

ICEs of change in concomitant therapies and other ICEs will always be considered as part of the treatment policy in the primary and all supplementary estimands. ICEs of this category will not affect the on-/off- treatment status which is only determined by changes in the study medication. These ICEs will be listed and summarized descriptively but will not be explicitly accounted for in the inferential analysis of efficacy.

Table 6.3: 1 Definition and technical specification of intercurrent events

[figure not shown]
Type of Intercurrent Event	Definition and Documentary Sources	Handling under the Primary Estimand
Temporary Tr	reatment Discontinuations or Interruption	ons
Exacerbation or acute episode of schizophrenia resulting in interruption of treatment	Identified from data collected in the Temporary Trial Treatment Discontinuation and Adverse Event pages of the CRF:  - Temporary discontinuation of trial treatment reported with reason being "Adverse Event", and  - AE category reported as "Schizophrenia Relapse" or MedDRA preferred term coded as "Schizophrenia"	Treatment policy

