Visit 6	Week 12	85	78 – 119
Visit 8	Week 18	127	120 – 140
Visit 9	Week 21	148	141 – 161
Visit 10	Week 24	169	162 – 175
Visit 11	Week 26	183	≥176

All post-baseline actual day windows will be curtained at the end of residual period if earlier than the specified upper bound in the table.

Table 6.7: 8 Analysis visit windows for weight and vital signs (on-treatment period)

Analysis Visit	Nominal Week	Planned Day	Actual Day Window
Baseline		1	≤1
Visit 2	Week 0 (post-baseline)	1	2 – 56
Visit 5	Week 9	64	57 – 119
Visit 8	Week 18	127	120–175
Visit 11	Week 26	183	≥176

All post-baseline actual day windows will be curtained at the end of residual period if earlier than the specified upper bound in the table.

[figure not shown]
Table 6.7: 9 Analysis visit windows for clinical laboratory evaluations, weight, and vital signs (post-treatment period)

Analysis Visit	Nominal Week	Planned Day	Actual Day Window (days after last dose)
Follow-up 2	14 days post-treatment	EOT + 14 days	13 – 19
Follow-up 4	21 days post-treatment	EOT + 21 days	20 – 26
Follow-up 6	28 days post-treatment	EOT + 28 days	>27

This analysis visit windows only apply to the post-treatment period defined in Table 6.1: 2

Table 6.7: 10 Analysis visit windows for PWC-20

Analysis Visit	Nominal Week	Planned Day	Actual Day Window (days after last dose)
Last value on treatment			<7
Follow-up 1	7 days post-treatment	EOT + 7 days	7 – 13
Follow-up 2	14 days post-treatment	EOT + 14 days	14 – 16
Follow-up 3	17 days post-treatment	EOT + 17 days	17 – 20
Follow-up 4	21 days post-treatment	EOT + 21 days	21 – 23
Follow-up 5	24 days post-treatment	EOT + 24 days	24 – 27
Follow-up 6	28 days post-treatment	EOT + 28 days	28 – 41
Post safety follow up			≥42

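### In the descriptive withdrawal analysis, patients who stop, have the early end-of-treatment visit and later restart have the drug-free gap counted as strictly on-treatment

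*Protocol*

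**What the plan says.** **Periods.** Protocol 7.2.5 plans a separate, descriptive analysis to identify AEs that are new after stopping compared with on treatment. The withdrawal period is days 1 to 28 after the last dose. The reference is the "Strictly on-treatment period for AEs occurring from the start of treatment to the last dose of trial medication". SAP Table 6.1: 2 repeats both, with the "Strictly on-treatment period" running from the date of first to the date of last administration. SAP 7.8.1 also assigns AEs by first and last administration. None of these places has a rule for a dosing gap.

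**Restart.** Protocol 6.2.3.4 covers early permanent discontinuation. It requires the eEOT visit and continues: "After the eEOT visit, patients should complete the safety follow-up visits". The same section adds: "Patients may choose to re-start the trial medication at any time during their planned treatment period", provided the investigator sees no safety concern. Under Protocol 5.2.6.2.1, collection for permanent discontinuers runs "until the 28 days after the early EOT visit: all AEs (serious and non-serious) and all AESIs".

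**PWC-20.** Under Protocol 5.2 the checklist "will be administered first at visit 10 or at the early EOT visit", and then during follow-up. SAP Table 6.7: 10 windows the forms by days after the last dose. The row "Last value on treatment" takes values below 7 days, and Follow-up 1-6 take days 7 to 41. Flow Chart footnote 17 waives the Visit 10 checklist for permanent discontinuers.

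**Gaps elsewhere.** SAP 6.3 does have a gap rule for interruptions: "the off-treatment period spans from the last treatment administration prior to the interruption + REP to the restart of the study medication". The title of Figure 6.3: 1 ties that on-/off-treatment status to the efficacy analysis.

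**The concern.** Both periods hang on one date, the last dose. For a patient who stops, goes through the withdrawal follow-up and then restarts, that date moves to the end of the second course. Every day of the gap precedes it. The gap therefore lies wholly inside the reference period and cannot lie in the withdrawal period, although the follow-up visits and AE collection after the first stop took place.

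Protocol Table 1.4.2:1 says that AEs after stopping have not been formally investigated, and this analysis is meant to look for them. In a restarter, an AE that appears after the first stop is placed in the reference. If the same AE returns after the final dose, it no longer looks new, although recurrence at each stop is what a withdrawal effect would look like. No efficacy result or error rate is involved.

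**Working it through.** The plan states no figure on this point, so there is none to reproduce. The check applies the written date rules to example patients. The dates are assumed; the rules come from Protocol 7.2.5, SAP Tables 6.1: 2 and 6.7: 10, and the Flow Chart.

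**1. Patient without a gap.** Doses on Days 1-182. Days 1-182 are strictly on-treatment and Days 183-210 are withdrawal, as intended.

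**2. Stop and restart.** Last dose before the stop on Day 60, eEOT Day 62, restart Day 95, final dose Day 182.
- Gap: Days 61-94 = 34 days. All 34 are at or before Day 182, so all are strictly on-treatment: 34/182 = 18.7%.
- Withdrawal period: Days 183-210. Of the first 28 days off drug (Days 61-88), 0 are in it.

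**3. Other restart dates, with the same stop and final dose.**

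| Restart day | Gap days | Counted strictly on-treatment | Counted withdrawal | Gap days within 28 days of the first stop |
|---|---|---|---|---|
| 70 | 9 (9/182 = 4.9%) | 9 | 0 | 9 |
| 75 | 14 | 14 | 0 | 14 |
| 90 | 29 | 29 | 0 | 28 |
| 120 | 59 | 59 | 0 | 28 |
| 170 | 109 | 109 | 0 | 28 |

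**4. PWC-20 in the patient of step 2.** Follow-up visits at eEOT + 7, 14, 17, 21, 24 and 28 fall on Days 69, 76, 79, 83, 86 and 90.
- Counted from the Day 60 dose: 9, 16, 19, 23, 26, 30. These fit the six follow-up windows in order (7-13, 14-16, 17-20, 21-23, 24-27, 28-41).
- Counted from the Day 182 dose, as the table is written: -113, -106, -103, -99, -96, -92. None enters Follow-up 1-6; all satisfy the below-7 condition of the on-treatment row.
- If the Visit 10 form is done (Day 169; 169 - 182 = -13), it is the latest form in that row and supplies the reference value. If it is not done, the latest is the Follow-up 6 form of Day 90, taken 30 days off drug.

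**5. Scale.** From Protocol 7.5: 30% to 40% early termination of 293 per arm, i.e. 0.30 x 293 = 87.9 to 0.40 x 293 = 117.2. The other rates are assumptions made only to show an order of magnitude.
- 2% to 10% of these restart: 1.8 to 11.7 per arm.
- 10% to 30% of restarters have an AE in the gap: 1.76 x 0.10 = 0.2 to 11.72 x 0.30 = 3.5 per arm.
- 20% to 50% of those have the same AE after the final dose: 0.18 x 0.20 = 0.04 to 3.52 x 0.50 = 1.8 per arm.

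**The case against.** **A rule may exist elsewhere.** SAP 7.8.1 says that AE analysis follows an internal guideline, which was not available. It might define the last dose for restarters. This stands: such a rule would close the point. On the visible text the plain reading is the final dose, because SAP 6.3 says so expressly when it means the dose before an interruption.

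**Other displays catch these events.** SAP Table 7.8.1: 1 has a category of abuse, dependence and withdrawal terms with its own table, and all gap AEs remain in the treatment-emergent tables. This stands, so a reader should not infer that the AEs disappear from the report. The category does not help with non-specific terms, which are what a comparison of periods is for.

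**The status may not be recorded.** A restarter who doses to Week 26 may look like a completer with an interruption, and the documents name no CRF field for a restart after permanent discontinuation. This stands, and the fix must not depend on a permanent or temporary label.

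**Illness may explain gap AEs.** Relapse or another AE can be the reason for a permanent stop, as it can for a temporary one. This also stands. It argues against pooling gap AEs into the withdrawal count, but not for leaving them in an on-drug reference.

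**The numbers are close to nil.** Probably so. The analysis is descriptive, the rule is the same in both arms, and the final dose still opens a full 28-day window.

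**Conclusion.** The point holds for one narrow group: patients who stop, have the eEOT visit and safety follow-up, and later restart. As written, their drug-free gap is counted as on-treatment and their first stop contributes nothing to the withdrawal period. Their PWC-20 forms from the first follow-up fall outside Follow-up 1-6.

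Two stronger readings are not supported. A reader might infer that the withdrawal analysis fails for early terminators in general; completers and early terminators who never restart are classified as intended. A reader might also infer that off-drug PWC-20 forms routinely become the on-treatment reference. That happens only if no Visit 10 form exists. Footnote 17 makes this possible, because it waives the form and does not say whether a restart reinstates it.

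The severity is minor. The number affected is unknown, because the documents give no restart rate; the 0.2 to 3.5 patients per arm above rests on assumed rates. The conclusion assumes that last dose means the final dose after restart and that the unseen guideline has no gap rule.

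**What to change.** First check the internal AE guideline. If it already covers restarts, a cross-reference in the SAP is enough. Otherwise, for the withdrawal-related analysis only:

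- Add a footnote to SAP Tables 6.1: 2 and 6.7: 10. Where an eEOT visit was done and drug was later restarted, the days from the first stop (the day after that dose) to the day before restart are excluded from the strictly on-treatment period, and PWC-20 forms from that gap are not used as the last on-treatment value.
- Identify these patients by the eEOT visit plus later dispensation, not by a CRF label. SAP Table 6.3: 1 already uses dispensation records for another purpose.
- List separately, with the reason for stopping, the AEs and PWC-20 values from day 1 after that dose to the earlier of day 28 or the day before restart. Do not pool them into the main withdrawal count.
- Leave temporary interruptions without an eEOT visit, and the main treatment-emergent AE tables, unchanged.

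In the example, the reference becomes 60 + 88 = 148 days. Days 61-88 (28 days) are listed and Days 89-94 (6 days) are in neither: 148 + 28 + 6 = 182. Because follow-up visits are timed from eEOT, the sixth PWC-20 form there falls on day 30, just past the listing limit; the sponsor should say whether to show it.

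The cost is one footnoted exception, one extra listing and the programming for them. The restart date may have to be taken from dispensation. The change should be settled before treatment codes are released (SAP 8).

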7.2.6 Other Analyses

Pharmacokinetic analysis

Plasma concentrations of Iclepertin at related time points will be analysed descriptively as further explained in Appendix 10.1.

7.2.7 Interim Analyses

No interim analysis is currently planned but safety will be monitored by an external and independent DMC.

7.3 HANDLING OF MISSING DATA

Every effort will be made to collect complete data at the specific time points, even for patients who terminated trial medication prematurely. If not specified otherwise, missing data are not imputed and remain missing. Potential outliers will be reported and analysed as observed.

For the primary estimand analysis of the primary efficacy endpoint using the mixed strategy for handling intercurrent events, if a patient misses a visit, the missing data will not be imputed. The MMRM analysis will handle missing data based on a likelihood method under the "missing at random" assumption.

MCCB endpoints

All imputations will be carried out separately for each study visit since there may be differences in test performance at different time points.

For the domains of Working Memory (consisting Letter-Number Span test and Wechsler Memory Scale 3rd ed. Spatial Span subtest) and the Speed of Processing (consisting Trail Making Test Part A, Brief Assessment of Cognition in Schizophrenia – Symbol Coding subtest, and Category Fluency test – animal naming), if only one of the tests consisting of a domain has missing value at a visit, the corresponding domain score can still be derived using the observed test raw score for that visit. If more than one of the tests consisting of a domain have missing value at a visit, the corresponding domain score is missing at that visit.

For the other five domains (Verbal Learning, Reasoning and Problem Solving, Visual Learning, Attention / Vigilance, and Social Cognition) which has only one test, if the test has missing value at a visit, the corresponding domain score is missing.

If a domain score is missing at a visit, the missing T-score of this domain can be imputed using the proprietary algorithm developed by MATRICS.

Page 85 of 112

Proprietary confidential information © 2023 Boehringer Ingelheim International GmbH or one or more of its affiliated companies

For baseline assessment, at least two-thirds of the cognitive domains (i.e., a minimum of five out of the seven domains for the MCCB overall composite score and a minimum of four out of the six domains for the MCCB neurocognitive composite score) need to be successfully assessed at baseline for it to be counted as a test occasion with non-missing baseline value.

For post-baseline assessments, at least half of the domains (i.e., a minimum of four out of the seven domains for the MCCB overall composite score and a minimum of three out of the six domains for the MCCB neurocognitive composite score) need to be successfully assessed to be considered a test occasion with non-missing value.

SCoRS endpoints

For the 20-item SCoRS assessment, if six or more of the 20 items have missing response, which includes the response of "N/A", for a patient at a visit, then the SCoRS total score for that patient at that visit is missing. If five or less of the 20 items have missing response, which includes the response of "N/A", for a patient at a visit, then the item with missing response will be imputed first with the average of the non-missing item values for the patient at the visit, and then SCoRS total score for the patient at the visit will be derived as the sum of the non-missing item values and the imputed item values.

PRECIS endpoints

The PRECIS scale consisted of 28 items, among which the first 26 items are coming from six domains, i.e., memory, communication, self-control, executive function, attention and sharpness of though, and the last 2 items measure overall degree of bother associated with all domains. For the aforementioned six domains, the maximum numbers of items allowed to be missing within each domain are 3, 1, 0, 0, 3 and 0, respectively, so that each domain would have at least 3 non-missing items. Within each domain, if the number of missing items exceed its allowable value, then the corresponding domain score would be considered missing, otherwise, the domain score is calculated as the average of the non-missing items scores under the domain. The PRECIS total score is calculated when not more than 7 items are missing overall, and the total score is calculated as the average of the non-missing item scores of the first 26 items.

A detailed description of the PRECIS items, the corresponding domains and the minimum number of non-missing items required for the domain scores is provided in Table 5.1:2.

Additional details on the handling of missing data will be specified in the TSAP prior to unblinding.

